3.4 Early Withdrawal /Discontinuation of the Study Treatment

A participant will be withdrawn from study treatment for any of the following reasons:

- Withdrawal of consent from the study by the participant at any time and for any reason. The reason for elective withdrawal will be documented in the research record if known.
- Unacceptable toxicity in the judgement of the Principal Investigator.
- Toxicity possibly related to abemaciclib does not resolve in14 days.
- Progression of disease requiring alternative systemic treatment.
- Significant participant or protocol noncompliance that, in the opinion of the Principal Investigator, warrants withdrawal of treatment. For example, participant is noncompliant in taking prescribed study medication or fail to return for scheduled follow up visits.
- Development of intercurrent, non-cancer related illnesses or complications that prevent either continuation of therapy or regular follow up.
- In the opinion of the Principal Investigator, it is inappropriate for the participant to continue on the study.
- Best medical interest of the participant at the discretion of the Principal Investigator.
- Subject becomes pregnant.
- Participant become lost to follow up. Participants who are unable to be located despite 3 documented attempts at contact (telephone, mail, or email) followed by a certified letter will be considered lost to follow up and rendered off study.
- Premature study closure.

Every effort should be done to help assure participants who are withdrawn from study treatment undergo the planned end of study follow up, end of treatment follow-up as outlined.3.4.1 Follow-up

An EOT visit will occur 30 ± 7 days from the last study treatment. Follow-up visits will occur every 3 months (\pm /- 7 days) x2, beginning 3 months after last dose of the study drug, then every 6 months (\pm 7 days) thereafter.

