7.2.3 Procedures During the End-of-Treatment Visit

For participants who complete the study or withdraw prematurely, final evaluations will be performed at the EOT visit or on the last day the participant receives the study drug.

Participants with ongoing AEs or clinically significant abnormal laboratory test results (as interpreted by the Principal Investigator) will be monitored per the Principal Investigator and AEs will be recorded and reported per protocol Section 10.1.2.

If a participant withdraws from the study during the treatment period, the reason must be determined and recorded on the participant's electronic case report form (eCRF). For participants who withdraw consent, every attempt will be made to determine the cause.

The following procedures will be performed at the EOT visit (up to 30 days \pm 7 days) from last dose of study drug), unless otherwise specified:

- Physical examination including body weight and vital sign measurements
- ECOG performance status
- AEs
- Concomitant medication
- Collect unused Abemaciclib
- Review participant drug diary and compliance with study medication
- Tumor evaluations through diagnostic imaging (CT/MRI/PET) every 8 weeks (± 3 days) until objective disease progression.
- Subsequent post-study treatment anti-cancer therapy
- Clinical laboratory tests
- 12-lead ECG if clinically indicated
- EORTC-QLQ-C30
- Extracellular vesicle detection will be performed every 8 weeks (± 3 days) until objective disease progression or study completion

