10.1.2 Recording and Reporting AEs

In this study, any AE occurring after the study participant has signed the informed consent form but *prior to* the initiation of study medication will be recorded as medical history. The commencement of AE collection will begin at the time of initiation of study medication (Cycle 1, Day 1). AE collection will continue up to and including the EOT visit. Those AEs that are determined to be related to the study treatment that are ongoing at the time of the EOT visit, will continue to be monitored until the event resolves or improves to baseline or Grade 1. For this study, the EOT visit may occur up to approximately 30 days after the last dose of study drug.

All AEs that occur during the defined study period must be recorded in the source documentation.

Signs and symptom will be recorded and entered into the database individually, except when considered manifestations of a medical condition or disease state. When such a diagnosis is made, all related signs, symptoms, and any test findings will be recorded collectively as a single diagnosis. A precise medical diagnosis will be recorded whenever possible.

Abnormal laboratory values or diagnostic test results will constitute AEs only if they induce clinical signs or symptoms or require treatment or further diagnostic tests. Disease progression will not be recorded as an AE.

When known, the onset and end dates, duration, action taken regarding study drug, and outcome for each AE should be recorded on the source documentation and entered in the study database. The guidelines relating to expectedness of each AE, relationship of each AE to study drug treatment and study procedures, and the severity and seriousness of each AE, as judged by the investigator, is described below.

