12.0 DATA HANDLING, DATA QUALITY ASSURANCE, AND RECORD KEEPING

12.1 Data Collection

Direct data entry into to the Penn State Cancer Institute OnCore CTMS will be utilized for this study. In addition to demographics, medical history, concomitant medications, and safety data, only those data needed to answer the study objectives will be included in the study database. The assessments and interventions noted in the *Protocol Required Interventions and Assessments* (Appendix B) will not be entered into the database. This data includes dates and results of physical examinations, vital signs, performance status, and laboratory results (CBC, Chemistry). Any abnormal results of the assessments will be captured as an AE according to the criteria noted in Section 10. Any concomitant medications administered for the purpose of procedures (anesthetics, etc.) will not be included in the data collection. AEs and SAEs will be recorded after the start of study drug until 30 days after discontinuation of study drug(s) or until a new anti-cancer treatment starts, whichever occurs first. AE that are ongoing at time will be checked or ongoing with no stop date. Unanticipated SAEs (ie. Serious, unexpected, and related (even remotely)) will be reported on the SAE Submission Form and entered in Oncore within 1 business day of discovery of the event. All other SAEs will be entered in the Oncore system within 5 business days. For screen failures (participants who sign the informed consent form but do not meet eligibility criteria), data relating to failure reason and demography will be captured.

Data will be reviewed for consistency by Data Management using both automated logical checks and manual review. The data collected will be reviewed and approved by the Principal Investigator or designated Co-investigator on an approximately quarterly basis depending on enrollment. Evidence of the Principal Investigator or Co-investigator review and approval may be done electronically in the OnCore CTMS. This approval acknowledges the Principal Investigator's review and acceptance of the data as being, to the best of his knowledge, complete, accurate, and current per the date documented on the form. Data will be verified using source documentation by the Study Monitor.

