| Dispense Abemaciclib | X | X | X | Abemaciclib is taken orally every 12 hours on days 1 through 28 of each cycle regardless of food intake. |
|------------------------------------|---|---|---|----------------------------------------------------------------------------------------------------------|
| Collection of Unused Study Drug | | X | X | |
| Study Drug Diary | | X | X | |
| Extracellular vesicles | X | | X | Every 8 weeks (±3 days) until disease progression or End of Treatment visit. |

Participants who are deriving clinical benefit after completing the treatment period may
continue on additional cycles of therapy at the discretion of the sponsor and medical monitor.
Any participant on abemaciclib after completing the treatment period will be monitored and
assessed for tumor response.

POST-TREATMENT FOLLOW-UP SCHEDULE OF ACTIVITIES

| | EOT a | Long-Term Follow-Up ^c | Instructions |
|------------------------------------------------------------------------|-------|-------------------------------------|--------------------------------------------------------------------------------------------------------------------------------|
| Physical Examination | X | | Including vital signs measurements (temperature, heart rate, respiration rate, blood pressure). |
| Weight | X | | |
| ECOG Performance Status | X | | |
| Adverse Events | X | | Only collected for unresolved AEs ≥ Grade 3 and related to the study drug. |
| Concomitant Medication | X | | |
| Collection of Unused Study Drug | X | | |
| Diagnostic Imaging –for Tumor Evaluation RECIST v.1.1 Reading | X | X | Every 3 months (± 7 days) beginning 3 months after last dose of the study drug for subjects who have not progressed. |
| Survival information | | X | Every 3 months (± 7 days) x2, beginning 3 months after last dose of the study drug then every 6 months (± 7 days) thereafter. |
| Post-Study Treatment Anti-Cancer Therapy | X | X | Every 3 months (± 7 days) x2, beginning 3 months after last dose of the study drug, then every 6 months (± 7 days) thereafter. |
| Hematology | X | | |

| Serum Chemistry | X | |
|------------------------------------|---|--|
| Coagulation Profile | X | |
| Urinalysis | X | |
| CA 19-9 | X | |
| 12-lead ECGb | X | |
| EORTC-QLQ-C30 | X | |
| Collection of Unused Study Drug | X | |
| Study Drug Diary | X | |
| Extracellular vesicles | X | |

^a End-of-treatment (EOT) visit will be completed up to 30 days (± 7 days) after last dose study drug. ^b as clinical indicated.

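### The protocol gives conflicting rules on when, and for which events, adverse-event collection ends after the last dose; they should be replaced by one window

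*Combined protocol and SAP*

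**What the plan says.** Six places bear on safety collection after the last dose.

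- **Section 10.1.2** ends collection at the EOT visit: "AE collection will continue up to and including the EOT visit". On timing it adds: "For this study, the EOT visit may occur up to approximately 30 days after the last dose of study drug". It gives no minimum delay and no cut-off for new therapy. Related AEs still ongoing at that visit are followed until they resolve or return to baseline or Grade 1.
- **Section 3.4.1** (the follow-up text within 3.4) dates the visit: "An EOT visit will occur 30 ± 7 days from the last study treatment".
- **Section 7.2.3** says that "final evaluations will be performed at the EOT visit or on the last day the participant receives the study drug". It then lists AEs, without restriction, among the EOT procedures: "The following procedures will be performed at the EOT visit (up to 30 days", with a ± 7 day allowance.
- **Section 12.1** has its own end point. AEs and SAEs are recorded "until 30 days after discontinuation of study drug(s) or until a new anti-cancer treatment starts, whichever occurs first".
- **Appendix B**, post-treatment schedule, footnote a, says the EOT "visit will be completed up to 30 days (± 7 days) after last dose study drug". The AE row of that schedule limits EOT collection to unresolved events of Grade 3 or higher that are related to study drug, and leaves the long-term follow-up column blank.
- **Section 1.3.3** says safety is assessed by evaluating AEs at the EOT visit and also at the follow-up visit. Section 7.2.4 lists only tumour evaluation, survival with cause of death, and subsequent therapy for follow-up visits.

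**The concern.** Site staff cannot tell from these texts when to stop asking about AEs, or which events to record at the EOT visit. Two participants with the same event on the same day after the last dose could be handled differently, and both in line with some part of the protocol.

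The loss is unlikely to be even across participants. Section 3.4 lists progression that requires another systemic treatment as a reason to stop study drug, and starting that treatment closes recording under section 12.1. Participants who progress and move on quickly therefore tend to have the shortest observation.

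Section 8.0 names confirming tolerability as a purpose of the study. Section 8.5.2 summarises the AEs collected and sets no analysis window of its own, so the safety tables inherit whatever window each participant happened to have.

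**Working it through.** **Inputs.** All are days after the last dose, taken from the sections above. I treat discontinuation in section 12.1 as the last dose. Let *e* be the day of the EOT visit and *t* the day new anti-cancer therapy starts.

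**Step 1. Reproduce each stated window.**

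| Source | Rule | Range (days) |
|---|---|---|
| 3.4.1 | EOT at 30 ± 7 | 30 − 7 = 23 to 30 + 7 = 37 |
| 7.2.3 and Appendix B footnote a | EOT no later than 30 (± 7), no minimum | 0 to 30 + 7 = 37 |
| 10.1.2 | collection ends at *e*; EOT no later than about 30, no minimum | 0 to about 30 |
| 12.1 | collection ends at min(30, *t*) | 0 to 30 |

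The union is 0 to 37 days. This is an outer envelope across several rules. The upper limit of 37 needs the end point of 10.1.2 combined with the visit timing of 3.4.1, 7.2.3 or Appendix B; 10.1.2 alone says about 30. The lower limit of 0 only reflects the absence of a stated minimum.

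**Step 2. Compare the end of collection under 10.1.2 (*e*) with that under 12.1 (min(30, *t*)).**

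- *e* < 23: allowed by 10.1.2, 7.2.3 and Appendix B, not by 3.4.1. Collection ends at *e* under 10.1.2 but stays open to day 30 under 12.1 if no new therapy starts.
- *e* from 23 to 30, no new therapy: all EOT rules are met, yet 12.1 keeps recording open for a further 30 − *e* days, between 0 and 7.
- *e* from 31 to 37: allowed by 3.4.1. Collection under 10.1.2 runs up to 37 − 30 = 7 days past the limit in 12.1.
- *t* < min(*e*, 30): 12.1 stops at *t*, while 10.1.2 continues to *e*.

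The two rules agree only when *e* = min(30, *t*).

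**Step 3. Compare which events are collected at the EOT visit.** Sections 10.1.2 and 7.2.3 include all AEs. The Appendix B row includes only events that are unresolved, related and Grade 3 or higher. A new Grade 2 event, or a new event judged unrelated, is recorded under the first two and not under the third.

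**Step 4. Check what remains after an early EOT visit.**

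- Related AEs ongoing at EOT: followed (10.1.2).
- SAEs the site learns of: reported to the sponsor within 24 hours of knowledge (10.3.1), with no end date in that sentence, and to the DSMC (table in 10.2.1).
- Death: survival and cause of death are collected (7.2.4).
- New-onset AEs and SAEs: 1.3.3 implies an evaluation at follow-up, but 7.2.4 and Appendix B schedule none, and the first follow-up contact is 3 months after the last dose.

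**Step 5. Scale.** The plan seeks 10 evaluable participants and may enrol about 20. One participant with an unrecorded event type shifts its observed rate by 1/10 = 10 percentage points, or 1/20 = 5 if 20 are treated. The documents do not say how many events to expect after the last dose, so the number lost cannot be estimated.

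**The case against.** The strongest reply is that the plan already holds a workable rule. Section 7.0 gives an EOT visit to everyone who completes or stops early, 3.4.1 puts it at 23 to 37 days, and 12.1 keeps AE and SAE recording open to day 30 unless new therapy starts. SAE and IND safety reporting in 10.3.1 has no end date in its wording. On that view the remaining differences are loose drafting.

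Part of this stands, and it rules out several stronger readings that a reader might infer.

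- **That collection may simply stop on the last dosing day.** Section 7.2.3 offers that day as an alternative to the EOT visit for final evaluations, whereas 10.1.2 ties collection to the visit itself. Day 0 is a permissive reading, not a rule. An argument from the stated 18.3 h half-life (5 × 18.3 = 91.5 h, about 3.8 days) depends on that reading and falls with it.
- **That a late related SAE has no way into the data.** Sections 1.3.3, 7.2.4, 10.1.2, 10.2.1 and 10.3.1 all provide some route.
- **That comparison with the cited abemaciclib breast-cancer trials would be favourably biased.** The figures there are deaths on treatment or within 30 days. Here survival is followed until death (section 7.0) and cause is collected, so such deaths are captured whenever AE collection ends. No comparison with those trials is planned.

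The reply does not remove the conflict. Reporting on knowledge depends on the site hearing of the event, and no enquiry is clearly scheduled after an early EOT visit. The immediate reporting of unanticipated AEs in 10.3.1 is itself limited to the protocol's AE observation period, which is the undefined quantity. The Appendix B restriction contradicts 10.1.2 on any reading of the dates.

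**Conclusion.** The point holds as a contradiction between sections that must be reconciled. Scheduled AE collection can end well before day 30 or as late as day 37, and the events eligible at the EOT visit range from all AEs to unresolved, related, Grade 3 or higher events only. The exposed group is participants with new-onset AEs or SAEs after an early EOT visit or after a quick change of therapy.

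This rests on the current wording and on the assumption that sites may follow any of the sections. It also assumes that progression often leads promptly to new treatment; section 3.4 suggests this but gives no figure. The direction is towards under-recording of late events, but its size is unknown. The primary response endpoint is unaffected. The correction should be made because tolerability is a stated aim, the sample is small and the remedy is cheap.

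**What to change.** State one data-collection window in sections 1.3.3, 3.4.1, 7.2.3, 10.1.2, 12.1 and Appendix B: all AEs and SAEs, of any grade and relatedness, with onset from the first dose through 30 days after the last dose, whatever the date of the EOT visit. Specifically:

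1. If the EOT visit, or the final evaluation on the last dosing day, falls before day 30, add a phone contact at day 30. An EOT visit after day 30 serves as that enquiry.
2. In Appendix B, remove the restriction on AEs at EOT for new-onset events within the window, and align footnote a with 3.4.1.
3. In 1.3.3, either remove AE evaluation at the follow-up visit or limit it to related AEs still ongoing, as 10.1.2 already provides.
4. Record the start date of new anti-cancer therapy. Preferably keep SAE recording open to day 30 after it starts. This is a secondary choice; the new-therapy cut-off could stay for non-serious AEs.
5. Define the AE observation period in 10.3.1 by reference to this window.

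The cost is a wording amendment and an occasional phone call. Some recorded SAEs will belong to the next therapy, but its start date allows them to be identified.

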^b Includes neutropenia, neutrophil count decreased.

^c Includes anemia, hematocrit decreased, hemoglobin decreased, red blood cell count decreased.

^d Includes platelet count decreased, thrombocytopenia.

^e Includes leukopenia, white blood cell count decreased.

Table 4: Laboratory Abnormalities for Patients Receiving Abemaciclib (Verzenio®) in MONARCH 1

| | VERZENIO N=132 | | |
|----------------------------|-------------------|--------------|--------------|
| | All Grades % | Grade 3 % | Grade 4 % |
| Creatinine increased | 98 | <1 | 0 |
| White blood cell decreased | 91 | 28 | 0 |
| Neutrophil count decreased | 88 | 22 | 5 |
| Anemia | 68 | 0 | 0 |
| Lymphocyte count decreased | 42 | 13 | <1 |
| Platelet count decreased | 41 | 2 | 0 |
| ALT increased | 31 | 3 | 0 |
| AST increased | 30 | 4 | 0 |

Creatinine Increased

Abemaciclib has been shown to increase serum creatinine due to inhibition of renal tubular secretion transporters, without affecting glomerular function. In clinical studies, increases in serum creatinine (mean increase, 0.2-0.3 mg/dL) occurred within the first 28-day cycle of abemaciclib dosing, remained elevated but stable through the treatment period, and were reversible upon treatment discontinuation. Alternative markers such as BUN, cystatin C, or calculated GFR, which are not based on creatinine, may be considered to determine whether renal function is impaired.

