7.3.8 Dose Delays/Modifications

Dose Modifications for Adverse Reactions

The recommended abemaciclib dose modifications for adverse events are provided in table below. Discontinue abemaciclib for participants unable to tolerate 50 mg twice daily. Once the drug is reduced, there is no dose re-escalation.

Abemaciclib Dose Modification for Adverse Reactions

| Dose Level | Abemaciclib Dose |
|---------------------------|--------------------|
| Recommended starting dose | 200 mg twice daily |
| First dose reduction | 150 mg twice daily |
| Second dose reduction | 100 mg twice daily |
| Third dose reduction | 50 mg twice daily |

Guidelines for Dose Adjustments and Delays of Abemaciclib

| Toxicity Type | Toxicity Profile and Severity | Dose Modification | Dose Reduction |
|--------------------------------------------------|----------------------------------|---------------------------------------------------------|------------------------------------------------------------------------------------------------------------------------------------------|
| Hematologic Toxicity | Grade 3 | Dose MUST be held until toxicity resolves to ≤ Grade 2. | Dose MAY be reduced by 1 dose level at investigator's discretion. |
| Hematologic Toxicity (second or more recurrence) | Grade 3 | Dose MUST be held until toxicity resolves to ≤ Grade 2. | Dose MUST be reduced by 1 dose level with each occurrence. Discontinue abemaciclib for participants unable to tolerate 50 mg twice daily |
| Hematologic Toxicity | Grade 4 | Dose MUST be held until toxicity resolves to ≤ Grade 2. | Dose MUST be reduced by 1 dose level. Discontinue abemaciclib for participants unable to tolerate 50 mg twice daily |

| Nonhematologic Toxicity (except diarrhea and ALT increased) | Persistent or recurrent Grade 2 that does not resolve with maximal supportive measures within 7 days to baseline or Grade 1 | Dose MUST be held until toxicity resolves to either baseline or ≤ Grade 1. | Dose MUST be reduced by 1 dose level. Discontinue abemaciclib for participants unable to tolerate 50 mg twice daily |
|----------------------------------------------------------------------|-----------------------------------------------------------------------------------------------------------------------------|----------------------------------------------------------------------------|-----------------------------------------------------------------------------------------------------------------------------|

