10.1 Adverse Events

10.1.1 Definition of an AE

An AE is any untoward medical occurrence in a participant administered a pharmaceutical product, regardless of whether it has a causal relationship with this treatment.

An AE can, therefore, be any unfavorable and unintended physical sign, symptom, or laboratory parameter that develops or worsens in severity during the course of the study, or significant worsening of the disease under study or of any concurrent disease, whether or not considered related to the study drug. A new condition or the worsening of a pre-existing condition will be considered an AE. Stable chronic conditions (such as arthritis) that are present before the participant signs the informed consent form and do not worsen during the study will not be considered AEs.

Accordingly, an AE can include any of the following:

- Intercurrent illnesses
- Physical injuries
- Events possibly related to concomitant medication
- Significant worsening (change in nature, severity, or frequency) of the disease under study or other pre-existing conditions. (Note: A condition recorded as pre-existing that is intermittently symptomatic [e.g., headache] and which occurs during the study should be recorded as an AE.)
- Drug interactions
- Events occurring during diagnostic procedures
- Laboratory or diagnostic test abnormalities that result in the withdrawal of the participant from the study, are associated with clinical signs and symptoms or an SAE, or require medical treatment or further diagnostic work-up, or are considered by the Principal Investigator to be clinically significant. Note: Abnormal laboratory test results at the screening visit that preclude a participant from entering the study or receiving study treatment are not considered AEs, but will be evaluated to monitor data from participants who do not meet screening criteria.
- All events of possible drug-induced liver injury with hyperbilirubinemia (defined as aspartate aminotransferase [AST] or alanine aminotransferase [ALT] ≥3 times the upper limit of the normal range [ULN], plus either bilirubin ≥2 times the ULN or international normalized ratio [INR]>1.5) or Hy's Law events require immediate study treatment cessation and reporting as a SAE.
- Disease progression (or progressive disease) or death due to disease progression will not be considered an AE or a SAE in this study, but will be collected as an efficacy assessment.

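### Sections 10.1.1 and 10.1.2 conflict on when a laboratory abnormality is an AE, and with Section 12.1 this lets Grade 3–4 cytopenias managed only by a dose hold or reduction drop out of both safety tables

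*Combined protocol and SAP*

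**What the plan says.** Section 10.1.1 opens with a broad definition under which a laboratory parameter that appears or worsens during the study can be an AE. Its list of examples then covers laboratory abnormalities that lead to withdrawal, that accompany symptoms or an SAE, that need treatment or further work-up, and those that "are considered by the Principal Investigator to be clinically significant".

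Section 10.1.2, on recording, is narrower. There such values "will constitute AEs only if they induce clinical signs or symptoms or require treatment or further diagnostic tests".

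Section 7.3.8 requires a hold for Grade 3 and for Grade 4 hematologic toxicity: "Dose MUST be held until toxicity resolves to ≤ Grade 2". It introduces its dose table as modifications for adverse events, and the dose-level table in 7.1.6 is titled as applying to Grade 3 or 4 AEs.

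Section 8.5.1 assesses safety and tolerability through AEs. Section 8.5.2 plans summaries of Grade 3 and 4 AEs, of treatment-related AEs and of AEs leading to withdrawal, and separately a count of participants with Grade 3 or 4 values.

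Section 12.1 says the Appendix B assessments are not entered in the database and names CBC and chemistry results among them. It then adds: "Any abnormal results of the assessments will be captured as an AE according to the criteria noted in Section 10".

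**The concern.** One event can be an AE under one section and not under the other. The clearest case is a symptom-free Grade 3 or 4 cytopenia managed by a hold or reduction alone, and neither section lists a hold or reduction as a criterion. Staff who follow the recording section would have grounds not to record it. Staff who follow the definition could record it if the Principal Investigator considered it significant.

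The pilot is meant to confirm tolerability (Section 8.0), and 10.1.2 attaches the action taken with study drug to AE records. If the AE record is missing, so are the grade, the attribution and the link to the dose change. With about 10 participants, one missed participant moves a reported rate by 10 percentage points (1/10).

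**Working it through.** **Step 1. The two rules side by side.**

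| Laboratory abnormality | 10.1.1 | 10.1.2 |
|---|---|---|
| Causes signs or symptoms | AE | AE |
| Needs treatment or further testing | AE | AE |
| Leads to withdrawal from the study | AE | Not listed |
| Associated with an SAE | AE | Not listed |
| Judged clinically significant by the Principal Investigator | AE | Not listed |
| Leads only to a dose hold or reduction | Not listed; can enter through the general definition or the significance criterion | Not listed; excluded by the only-if wording |

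The 10.1.1 list is illustrative, so an unlisted case stays open. The 10.1.2 sentence is exclusive, so an unlisted case is out. Rows 3 to 5 are a direct conflict, and row 6 is a gap that the two sections treat differently. Row 3 also bears on a planned output, the summary of AEs leading to withdrawal.

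**Step 2. Does the table of values cover the gap?** The 8.5.2 count of Grade 3 or 4 values needs graded laboratory data. Section 12.1 names CBC and chemistry as not entered and gives one route in for abnormal results, as AEs under Section 10. A cytopenia excluded by 10.1.2 therefore has no stated database source for the values table either.

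**Step 3. Scale.** The plan gives no figure on this point, so there is none to reproduce. The inputs are the tables for the 200 mg twice daily monotherapy breast cancer study in the protocol background. The Table 4 row reads "Neutrophil count decreased | 88 | 22 | 5" (percent: all grades, Grade 3, Grade 4). Applying these rates to biliary tract cancer is an assumption.

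- Grade 3–4 neutrophil decrease: 22% + 5% = 27%.
- Expected in 10 participants: 10 × 0.27 = 2.7. In 20: 20 × 0.27 = 5.4.
- Chance of at least one in 10: 1 − 0.73^10 = 0.957.
- Chance of at least one among the 5 whose recruitment triggers the safety review: 1 − 0.73^5 = 0.793.

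**Step 4. Effect of incomplete recording.** If a share *q* of these events is recorded (assumed, participants independent), the chance that the AE table shows none in 10 is (1 − 0.27*q*)^10:

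| *q* | P(0 of 10 in the AE table) |
|---|---|
| 100% | 0.043 |
| 75% | 0.104 |
| 50% | 0.235 |
| 25% | 0.497 |

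**Step 5. How far laboratory and AE tables can differ.** In the same study:

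| Parameter | Laboratory table (Table 4) | Adverse reaction table (Table 3) |
|---|---|---|
| Neutrophils, Grade 3–4 | 22% + 5% = 27% | 19% + 5% = 24% |
| White cells, Grade 3 | 28% | 5% |

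For neutrophils the AE rate is 24/27 = 89% of the laboratory rate. For white cells it is 5/28 = 18%; in 10 participants that is 2.8 against 0.5 expected, and a chance of at least one of 0.963 (1 − 0.72^10) against 0.401 (1 − 0.95^10). The documents do not give that study's AE recording rule, so this shows only that the loss can be small or large depending on the parameter.

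**The case against.** The strongest reply is that the protocol elsewhere treats these events as AEs. Sections 7.1.6 and 7.3.8 label the toxicities that trigger dose modification as adverse events, and an investigator applying those tables would probably record one. The opening definition and the significance criterion in 10.1.1 can both admit such a value. Even under 10.1.2, a cytopenia needing growth factors (7.4.4.1) requires treatment, and a repeat count taken to document recovery might be read as a further diagnostic test.

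Much of this stands, and it rules out two stronger readings. A reader might infer that neither section counts an abnormality whose only consequence is a hold. The documents do not support that, because only 10.1.2 excludes it. A reader might also infer that the AE table would show none of these events under 10.1.2 and all of them under 10.1.1. That needs every event to be symptom-free, untreated and not further tested, and then every one to be judged significant; nothing in the documents supports this, and the 27% against 24% for neutrophils points the other way.

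The reply does not remove the conflict. The AE labels in Section 7 contradict the recording rule and do not override it. Counts are already scheduled every 2 weeks for the first 2 months (7.1.6), so the next routine count is not clearly a further test.

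It can also be said that laboratory results are a safety endpoint (1.3.3), that the Principal Investigator reviews them (10.0), that the safety committee sees all safety data after 5 participants (8.6), and that 12.1 admits safety data in general terms. The values also remain in the source records. So the values table could still be built, but 12.1 as written does not provide for it.

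**Conclusion.** The concern holds in a limited form. Sections 10.1.1 and 10.1.2 conflict. The recording rule excludes, and the definition leaves to judgement, a Grade 3–4 cytopenia whose only consequence is a dose hold or reduction. Because 12.1 keeps CBC and chemistry results out of the database, the values table in 8.5.2 has no secured source, and such an event can be absent from both safety tables.

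If the 27% rate carried over, about 2.7 of 10 participants would have a Grade 3–4 neutrophil decrease, with a 96% chance of at least one. That is the number at risk of inconsistent recording and not an estimate of the number lost, which depends on the parameter and on local practice.

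This should be fixed, but it does not threaten the trial's main result. The response rate is unaffected, and no stopping rule in 7.1.9 is tied to a count of Grade 3–4 AEs.

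**What to change.** 1. Delete the only-if sentence in 10.1.2 and use one laboratory AE rule in both sections. Keep the 10.1.1 criteria and add any abnormality that leads to a dose hold, reduction or discontinuation.
2. Reconcile 12.1 with 8.5.2 so that Grade 3–4 laboratory values are entered in the database whether or not they are also AEs.

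Making every Grade 3 or higher value an AE automatically would be a further convention that neither section implies. It is not needed if both changes are made.

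The cost is a few sentences, some more AE and laboratory records, and slightly less favourable AE tables. The change concerns recording only; no dose or treatment rule is altered.
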